twenty-one people, approximately 60% of whom reported currently receiving or having received mental health services. Analysis of the in-depth interviews and ethnographic field notes revealed four major characteristics of the musical intervention space and music making experience: 1) the importance of a nonclinical therapeutic and sober environment; 2) opportunities for social engagement and integration; 3) opportunities for identity (re)invention; and 4) an outlet for artistic and musical expression. For this proposal, we have adapted that MI to facilitate the examination of predictive coding relevant mechanisms. We term this adapted intervention **SING – Song-Making In a Group**. In a one-hour session, 5 individuals work together with a trained facilitator to experience and/or produce music. We propose to manipulate the SING group tasks to identify the impact of certain activities on AVH and social processing.

Our SING Team is unique, uniting people with lived experience of psychosis, quantitative and qualitative researchers, clinician scientists, and musicologists. This unity is made possible by the **Connecticut Mental Health Center**, a state mental health facility whose tripartite goals are treatment, education and research and whose unique partnership with Yale University is embodied in the two research centers connected by this application; the *Yale Program for Recovery and Community Health* and the *Clinical Neuroscience Research Unit in the Abraham Ribicoff Research Facilities*. Together these units have the real and virtual infrastructures, staff and experience to make the proposed work a success. We make this claim confidently, because the key players already collaborate, and the interventional musicologists are already active and successful in the Connecticut Mental Health Center.

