		ACTIVE	
		-	+
OWNERSHIP	-	Listening (pop music) n=50	Karaoke (no recording) n=50
	+	Listening (curated playlists) n=50	SING (producing, performing) n=50

Figure 6. R33 Design

R33 Phase: Should we demonstrate a meaningful impact of SING on computational metrics of behavior, we will proceed to use those metrics in the R33 phase where we aim to deconstruct the active ingredients of SING along two key dimensions, Activity (whether engagement with the group is active or passive) and Ownership (creating some novel musical product, or not). Following screening, once participants have been deemed eligible, their behavior on the selected behavioral metrics will be assayed and they will be randomized to an intervention group. Performance on our computational metrics will be balanced across intervention groups prior to commencement of the four interventions (total n=200, n=50 per intervention, 10 groups of 5 participants per intervention):

- (1) **Passive Listening without Ownership** (Activity - / Ownership -, n=50). The group will meet on four occasions, once a week for two hours. The trained facilitator, having procured a playlist of popular music, will spend 15 minutes introducing the session, reminding participants not to sing along and to just sit quietly listening to the music. Next, the facilitator will play music from the playlist through a high-quality speaker at 60-75 decibels for 90 minutes. In the final 15 minutes, the facilitator will summarize the session and dismiss the participants, sharing follow-up music opportunities at the end of the fourth and final session.

- (2) **Passive Listening with Ownership** (Activity - / Ownership +, n=50). The trained facilitator will provide a computer and speaker with the ability to stream songs through many media outlets (i.e., Spotify, YouTube, Google). In the first fifteen minutes, the facilitator will introduce the session, participants are reminded not to sing along and to just sit quietly listening to the music. Next the participants will choose songs that they would like to hear. The list can be edited at any point. For the next 90 mins, the playlist will be played through a high-quality speaker at 60-75 decibels. In the final 15 minutes, the group will be concluded, and the participants will be dismissed. If it is the final session, they will be offered follow-up information about the musical opportunities.

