- (3) **Karaoke** (Activity +/ Ownership -, n=50). The trained facilitator will provide a microphone and speaker along with a karaoke playlist of music and a screen to view lyrics. In the first 10 minutes, participants will be encouraged to write down a list of songs that they would like to sing to. The list can be edited at any point. For 5 minutes, they will conduct body and vocal warm ups, listening to self and others. For 90 minutes, the facilitator will order the participants in turn and invite them to perform karaoke at 60-75 decibels. Each participant will be encouraged to participate. For the final 15 minutes, the session will be concluded, and if the final session, participants will be informed of local opportunities to engage further with music making and musical experiences.

[figure not shown]

Figure 7. Behavioral simulation across three iterations of the HGF. 1) (top panel) standard HGF implementation; 2) (middle panel) adding Nu, which codes the weighting between sensory evidence and perceptual beliefs; 3) (bottom panel) allowing a more flexible influence of Nu on the overall model. Simulated responses were then compared with observed behavior, comparing the proportion of identical responses (left), individual phi coefficients (middle), and proportion of “yes” responses (right).

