- (4) **SING** (Activity +/- Ownership +, n=50). As in the R61, the trained facilitator will provide a keyboard, professional microphone, recording interface, headphones, guitar, computer and a Digital Audio Workstation (DAW) for recording. The first 10 minutes of group involve introductions to the other participants and facilitator as well as the goals of the session. Participants will be given paper and a pencil with which to brainstorm potential lyrics. The next 5 minutes involve body and vocal warm ups, listening to self and others. For the next 90 minutes, participants will work together with the facilitator and independently to create their own original lyrics and melody. Each song will have at least one collaborative section (usually the chorus) where lyrics are written and performed together by the whole group. Participants also can write alone and perform sections by themselves. For the last 10 minutes, the group listens back to the entire song that they created. In the final 5 mins, the session is concluded, and the group disbands until the next session. If it is the final session, information sheets on local studio opportunities, karaoke nights and other opportunities to produce, perform and experience music.

For all four intervention types, at the end of each session, the facilitator notes level of contribution and any other significant points regarding individual participation and group coherence (these may be used to weight each participant's contributions to analyses of the intervention's impact on computational behavioral endpoints

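### In the R33 session outlines only SING schedules introductions between participants, so any effect of introductions could bias both main effects and the interaction; a common opening would remove this difference

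*Combined protocol and SAP*

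**What the plan says.** The four R33 interventions are outlined in Section I, item 13 (Statistical Considerations, R33 Phase), in segments of 5 to 90 minutes. The openings differ:

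- SING, arm (4): "The first 10 minutes of group involve introductions to the other participants and facilitator as well as the goals of the session". Paper for lyric ideas and warm-ups follow.
- Karaoke, arm (3): "In the first 10 minutes, participants will be encouraged to write down a list of songs that they would like to sing to". Warm-ups follow.
- Listening without ownership, arm (1): the facilitator "will spend 15 minutes introducing the session, reminding participants not to sing along and to just sit quietly listening to the music".
- Listening with ownership, arm (2): "In the first fifteen minutes, the facilitator will introduce the session, participants are reminded not to sing along". Participants then choose songs, with no time allotted to that step.

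The same section defines the two factors as "Activity (whether engagement with the group is active or passive) and Ownership (creating some novel musical product, or not". Of the session schedule it says, under arm (1), "The group will meet on four occasions, once a week for two hours"; the R61 description of SING, to which arm (4) refers back, gives the same number and length. Within the 90-minute SING block, "Each song will have at least one collaborative section (usually the chorus) where lyrics are written and performed together by the whole group".

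Under R33 Power to Detect Effects, the analysis is a 2x2 analysis of variance on Activity and Ownership. Any of the R61 tasks may or may not be carried forward. Under Robustness and reproducibility, the SING and control interventions are still to be manualized.

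**The concern.** R33 is meant to find which ingredient of SING matters, so the arms should differ, as far as possible, only in Activity and Ownership. Being introduced to the other group members is not the creation of a musical product, so it is not Ownership. It might be read as active engagement with the group, but Karaoke is also an active arm and its outline does not list it. On either reading, the two active arms differ in something other than Ownership.

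The plan gives some reason to care about social content. Its Background on SING reports "opportunities for social engagement and integration" as one of four major characteristics of the existing music programme, separate from artistic expression. It also hypothesizes that musical intervention reduces social learning deficits. If introductions had any effect, R33 would credit it to Activity, Ownership or their interaction. Because the component coincides exactly with one cell, no later analysis could take it out.

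**Working it through.** **Inputs.** From the R33 Phase text: 50 participants per cell, 200 in total, with the four openings as above. From R33 Power to Detect Effects: difference 0.01, SD 0.02, two-sided 0.05, 80% power, at least 31 participants. Not in the documents: the effect b of introductions on any endpoint. It is assumed below, over a range of 0 to 0.01.

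**The plan's own figure.** The paired normal approximation gives n = ((1.960 + 0.842) × 0.02 / 0.01)² = 31.4. This agrees with the stated 31 (rounding up gives 32) and shows that 0.02 is being used as the SD of the pre-post change. The present point does not depend on that sample size; it only borrows the 0.01 and 0.02 as a scale.

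**Session time.**

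- SING: 10 + 5 + 90 + 10 + 5 = 120 minutes.
- Karaoke: 10 + 5 + 90 + 15 = 120 minutes.
- Listening arms: 15 + 90 + 15 = 120 minutes, leaving out the untimed song-choosing step in arm (2).

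The SING opening is 10/120 = 8.3% of a session. Over four sessions it is at most 40 of 480 minutes, and part of that goes to session goals.

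**Effect on the contrasts.** Let introductions add b to the mean change in the SING cell and nothing elsewhere, with no true Activity or Ownership effect. The cell means are Pop 0, Curated 0, Karaoke 0, SING b.

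- Activity = (Karaoke + SING)/2 − (Pop + Curated)/2 = b/2
- Ownership = (Curated + SING)/2 − (Pop + Karaoke)/2 = b/2
- Interaction = (SING − Karaoke) − (Curated − Pop) = b

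**Chance of a false finding.** Take participants as independent and the SD of change as 0.02. The standard error of a main effect (100 against 100) is 0.02 × √(1/100 + 1/100) = 0.00283. That of the interaction is 0.02 × √(4/50) = 0.00566, twice as large. The ratio of shift to standard error is therefore the same for all three contrasts, and so is the rejection probability.

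| Assumed b | Shift in each main effect | Shift in interaction | Rejection probability (nominal 5%) |
|---|---|---|---|
| 0 | 0 | 0 | 5.0% |
| 0.002 | 0.001 | 0.002 | 6.4% |
| 0.004 | 0.002 | 0.004 | about 11% |
| 0.005 | 0.0025 | 0.005 | 14.3% |
| 0.01 | 0.005 | 0.01 | 42.4% |

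The last row sets introductions equal to the whole effect the plan expects of SING. It is an upper bound for illustration.

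**After equalizing.** If all four arms have the same introductions and their effect is additive, every cell mean gains b, and all three contrasts return to 0.

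**The case against.** These are short outlines, and silence is not exclusion. Fifteen minutes is more than a reminder not to sing along needs, and facilitators in the other three arms may well have people introduce themselves. A reader might infer that introductions will happen only in SING; the documents show only that they are scheduled only there. This stands, and it limits the point to what the text prescribes.

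A reader might also infer that introductions lie wholly outside both factors. The definition of Activity as engagement with the group does not support that. If introductions are counted as Activity, the shift in the Activity effect is open to argument. The shifts in Ownership and the interaction are not, because Karaoke lacks the component.

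A third tempting inference is that R33 is shown to be biased, chiefly on social learning. The documents give no effect of introductions on anything. The 0.01 scale belongs to a conditioned-hallucination model parameter, and no scale is given for social learning. The partner in the social task is a confederate, not a group member. The finding on social engagement comes from interviews and observation at a drop-in site. The endpoint enters R33 only if it meets the go/no-go rule. All arms also meet in groups of five, so acquaintance with the others is not unique to SING.

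Finally, whole-group lyric writing and performance is a larger social component listed only for SING, and equalizing the opening leaves it in place. That is correct. But it is part of making the group's song and cannot be removed without changing the intervention, whereas the difference in openings is incidental and avoidable.

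**Conclusion.** The point holds in a limited form. As outlined, SING is the only R33 arm with scheduled introductions between participants. Any effect b of them could shift each main effect by b/2 and the interaction by b, with no term in the planned analysis to separate it. The size of b is unknown and may be zero. The rejection probabilities rest on an assumed b, an SD of change of 0.02, independent participants, 50 completers per cell and no true factor effects; they illustrate the mechanism and do not estimate a bias in this trial.

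This is a cheap improvement to make before the manuals are written. It is not a demonstrated flaw in the R33 results.

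**What to change.** In the four R33 arm descriptions and in the manuals, give every arm the same brief introductions of participants and facilitator, at the same sessions, inside the existing 10 to 15 minute opening. The arm-specific steps then follow: song list, session goals and lyric paper, or the instruction to listen quietly. Leave the 90-minute blocks unchanged. State that whole-group song writing remains specific to SING, and acknowledge this when Activity, Ownership and interaction effects are interpreted.

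The change is one of wording, with no added session time, staff or participants. The cost is less opening time for the Karaoke song list, which the plan lets participants edit at any point, and for SING's session goals and lyric brainstorming. The introductions need to be short: a full 10 minutes would use up the whole Karaoke song-list slot.

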SING Intervention (R61). A trained musician-facilitator will convene a series of four weekly two-hour sessions to which groups of five participants will be invited (total n=50 participants, or n=10 groups). The groups will be convened at the Connecticut Mental Health Center for convenience (though other locations may be employed). The facilitator provides keyboard, professional microphone, recording interface, headphones, guitar, computer and a Digital Audio Workstation (DAW) for recording. The first 10 minutes of group involve introductions to the other participants and facilitator as well as the goals of the session. Participants will be given paper and a pencil with which to brainstorm potential lyrics. The next 5 minutes involve body and vocal warm ups, listening to self and others. For the next 90 minutes, participants will work

together with the facilitator and independently to create their own original lyrics and melody. Each song will have at least one collaborative section (usually the chorus) where lyrics are written and performed together by the whole group. Participants also have the ability to write alone and perform sections by themselves. For the last 10 minutes, the group listens back to the entire song that they created. In the final 5 mins, the session is concluded, and the group disbands until the next session. Post-session, the facilitator notes level of contribution and any other significant points regarding individual participation and group coherence (these may be used to weight each participant's contributions to analyses of the intervention's impact on computational behavioral endpoints). Finally, we appreciate that it is crucial to provide continued opportunities for engagement with MI after the conclusion of the group, should the participants desire. In the final session, participants will be provided with information sheets on local studio opportunities, karaoke nights and other opportunities to produce, perform and experience music.

R61 Aim 1 Conditioned Hallucinations:

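### The option to weight the impact analyses by facilitators' contribution notes would replace R33's randomised contrasts with ones that can be biased in either direction

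*Combined protocol and SAP*

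**What the plan says.** The option appears twice: in Section I, item 4 (Research Plan), under SING Intervention (R61), and in Section I, item 13 (Statistical Considerations), after the four R33 arm descriptions. In both places, once the session is over, "the facilitator notes level of contribution and any other significant points regarding individual participation and group coherence (these may be used to weight each" participant). The purpose is given in full as "these may be used to weight each participant's contributions to analyses of the intervention's impact on computational behavioral endpoints". The R33 paragraph covers every arm: "For all four intervention types, at the end of each session, the facilitator notes level of contribution".

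Four other statements in item 13 bear on this:

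- **Timing.** After eligibility and baseline testing, "they will be randomized to an intervention group". The sessions, and therefore the notes, come later.
- **Listening arms.** In the pop-music arm the facilitator opens by "reminding participants not to sing along and to just sit quietly listening to the music". In the curated-playlist arm "participants are reminded not to sing along and to just sit quietly listening to the music", but they also pick the songs and may change the list during the session.
- **Active arms.** In Karaoke, "Each participant will be encouraged to participate". In SING, participants write and perform an original song.
- **Analysis.** R33 Power to Detect Effects names a 2x2 analysis of variance on Activity and Ownership. The R61 power paragraph names paired t-tests. Neither mentions weights.

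The plan gives no rating scale, weighting formula or rule for deciding whether to weight. It contains no statement that the primary analysis is unweighted or that participants are analysed in the arm assigned.

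**The concern.** Randomisation makes the four R33 arms comparable when every participant counts equally in the arm assigned. A weight recorded after the sessions is itself partly a result of the assignment. The arm instructions tie contribution to Activity, one of the two factors under test. The rater runs the group and so knows the condition; the documents do not discuss blinding, but the role settles this.

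Weighting by such a variable gives low contributors less say, like a soft per-protocol analysis whose selectivity can differ by arm. If contribution is related to change, and that relation or the spread of the weights differs between arms, the difference between weighted arm means contains a part that is not an intervention effect.

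The wording is also permissive and undefined. Whether to weight, and how, could be settled after the results are seen. At stake are the contrasts that R33 is designed to estimate.

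**Working it through.** **1. Inputs from the plan (item 13).** Pre-post difference 0.01 units; standard deviation 0.02; two-sided 0.05; 80% power; 50 per arm, so Activity compares 100 with 100.

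**2. The plan's own figure.** (1.960 + 0.842)² × (0.02/0.01)² = 31.4, which agrees with the stated 31. This takes 0.02 as the SD of the change, and I use it in that sense. The sample size is not disputed here.

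**3. Inputs not in the plan (assumed).** r is the within-arm correlation between weight and change. CV is the coefficient of variation of the weights. I take r = 0.3 (also 0.1 and −0.3) and CV = 0.5 in the active arms, and vary the listening arms.

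**4. Formulas.**

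- Shift in a weighted arm mean = Cov(w, y)/E(w) = r × CV × SD.
- Effective size of an arm = n/(1 + CV²).

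At r = 0.3 and CV = 0.5 the shift is 0.3 × 0.5 = 0.15 SD, or 0.15 × 0.02 = 0.003 units (30% of 0.01). An arm of 50 has effective size 50/1.25 = 40; this loss occurs even when r = 0.

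**5. Shifts in the contrasts.** Activity is the average of SING and Karaoke minus the average of the two listening arms. Ownership is the average of SING and curated playlist minus the average of Karaoke and pop music.

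- Both listening arms flat: Activity 0.15 − 0 = 0.15 SD; Ownership 0.075 − 0.075 = 0.
- Curated arm varies like the active arms: Activity 0.15 − (0.15 + 0)/2 = 0.075 SD; Ownership 0.15 − (0.15 + 0)/2 = 0.075 SD.
- Both listening arms at CV = 0.3: Activity 0.15 − 0.3 × 0.3 = 0.06 SD; Ownership 0.
- All arms alike: both 0.

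**6. Type I error for Activity, no true effect.** Worked example with both listening arms flat: SE = √(1/80 + 1/100) = 0.15 SD, so the shift is 1.0 SE. Rejection is Φ(−0.96) + Φ(−2.96) = 0.17. The other rows use the same method, and simulation gives similar values.

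| Case | Activity shift | By hand | Simulated, robust SE |
|---|---|---|---|
| r = 0.3, both listening arms flat | 0.15 SD (0.003) | 17% | about 15–16% |
| r = 0.3, curated arm varies too | 0.075 SD (0.0015) | 8% | about 8% |
| r = 0.3, listening arms CV 0.3 | 0.06 SD (0.0012) | 7% | 6.7% |
| r = 0.3, all arms alike | 0 | 5% | 5.1% |
| r = 0.1, both listening arms flat | 0.05 SD (0.001) | 6% | 6.5% |
| r = −0.3, both listening arms flat | −0.15 SD (−0.003) | 17% | 16% |

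The choice of standard error matters. Ordinary weighted least squares gives 18% in the first row and 7.6% at r = 0.1. The unweighted comparison was unbiased, with error near 5%, in every case simulated. Clustering within groups of five was not modelled.

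**The case against.** The strongest reply is that the plan does not commit to weighting. The analyses it names are paired t-tests and a 2x2 analysis of variance, neither described as weighted. The protocol also presents R33 as a mechanistic study, not an efficacy trial, so asking how engagement relates to change is legitimate. Both points stand. They support an engagement analysis with a defined, secondary status; they do not support an undefined option attached to the impact analyses.

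A reader might infer three stronger things that the documents do not support:

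- **That weighting necessarily biases Activity, and upwards.** The bias is zero if contribution is unrelated to change, cancels if correlation and spread match across arms, and reverses if the correlation is negative. The documents fix none of these.
- **That contribution can hardly vary in either listening arm.** This is plausible for pop music. In the curated-playlist arm participants choose and edit the songs, and the notes also cover group coherence, which can differ anywhere. Variation in that arm halves the Activity shift and puts an equal shift into Ownership.
- **That weighting inflates the R61 Go decision.** R61 is single-arm, so there is no randomised comparison to bias; weighting only changes which mean change is estimated. The Go/No Go text does not say that weights apply. Its threshold is a change of two standard deviations, so if the SDs are comparable a 0.15 SD shift is 0.15/2 = 7.5% of it.

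**Conclusion.** The point holds in conditional form. If the option is used in R33, the weighted contrasts are no longer randomised comparisons. Activity, and Ownership if ratings vary in the curated arm, can be biased in either direction whenever contribution correlates with change and its spread or correlation differs between arms. The arm instructions make such a difference likely but do not establish it.

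At the assumed r = 0.3 and active-arm CV = 0.5, the plausible range is no Activity shift to 0.15 SD, with type I error from about 5% to about 15–16%. At r = 0.1 the error is about 5–7%, close to nominal. These sizes rest entirely on the assumed r and CV. What is certain from the text is that the weight is post-randomisation, undefined and optional, and that no unweighted as-assigned primary analysis is stated to guard against it.

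**What to change.** In both places (item 4, SING Intervention (R61); item 13, the paragraph after the four R33 arms), remove the weighting from the impact analyses. Under R33 Power to Detect Effects, state that the primary 2x2 analysis is unweighted, with every participant in the assigned arm; in the R61 power paragraph, state that the paired tests are unweighted. Keep the contribution notes as process data, or for an engagement analysis within arms that is labelled exploratory and has a rating scale defined in advance.

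The cost is a sentence in each place. Data collection and sample size do not change. The one real downside is that engagement-weighted results become exploratory only.

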R33 Power to Detect Effects. Since all participants will perform all tasks; Conditioned Hallucinations, Social Learning and Linguistic Markers, we powered the R33 based on our own preliminary data (on the understanding that any and all of the tasks from the three R61 aims may or may not progress to the R33). Estimated effects for our proposed study of the impact of SING on conditioned hallucinations model parameters are based upon our own data in **Figure 2**. If SING can curtail these group differences – i.e. decrease hallucinating patient responses to the level of non-hallucinating controls, then we would predict the true difference in HGF model parameters pre- versus post-SING would be 0.01 arbitrary units and the within-patient standard deviation of the parameter estimates would be 0.02. We will analyze the model parameter specific to each of the four interventions in a 2x2 design (Activity vs Ownership) using Analysis of Variance, leveraging the added power of within-participants designs. We estimate we will need at least 31 participants to have 80% power to detect a treatment difference at a two-sided 0.05 significance level⁵⁴. We budgeted for 50 unique participants per group to allow for participant drop-out and the detection of smaller effects of SING on conditioned hallucination behavior, social learning and language use.

Robustness and reproducibility (both phases). We have built in a replication study of the effects of SING on conditioned hallucinations, social learning and language use across our R61 and R33 studies (should those metrics satisfy our Go/No-Go criteria). We have chosen to focus on metrics with face and construct validity for psychosis, whose implication in the mechanisms of psychosis have been conceptually replicated across labs in different cities⁵⁷ and countries⁵⁸. Our tasks, analysis code, and data will be made freely available via Yale's ModelDB site. We will optimize and manualize the SING and control interventions in order to prosecute the R61 and R33. Those manuals will be available open access also.

SECTION II: RESEARCH INVOLVING DRUGS, BIOLOGICS, RADIOTRACERS, PLACEBOS AND DEVICES

If this section (or one of its parts, A or B) is not applicable, check off N/A and delete the rest of the section.

- A. RADIOTRACERS N/A
- B. DRUGS/BIOLOGICS N/A
- C. DEVICES N/A

SECTION III: RECRUITMENT/CONSENT AND ASSENT PROCEDURES

1. Targeted Enrollment: *Give the number of subjects.*

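### The R33 sample-size statement reuses R61's one-group figure of 31 and states no Activity or Ownership effect; on its own inputs, 50 per arm gives at most 42% power for the smaller factor

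*Combined protocol and SAP*

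**What the plan says.** The relevant text is in Section I, item 13.

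- **R61 Statistical Power** sizes a one-group study analysed by paired t-tests: pre/post change 0.01, SD 0.02, 31 participants, 80% power, two-sided 0.05.
- **R33 Power to Detect Effects** repeats those inputs. It assumes that "the true difference in HGF model parameters pre- versus post-SING would be 0.01 arbitrary units" with the same SD of 0.02, and concludes: "We estimate we will need at least 31 participants to have 80% power to detect a treatment difference". The analysis is now given as: "We will analyze the model parameter specific to each of the four interventions in a 2x2 design (Activity vs Ownership) using Analysis of Variance". The same sentence describes this approach as "leveraging the added power of within-participants designs". On arm size it says: "We budgeted for 50 unique participants per group to allow for participant drop-out", and that this also allows smaller effects of SING to be detected.
- **R33 Phase** gives the purpose: "we aim to deconstruct the active ingredients of SING along two key dimensions", namely Activity and Ownership. After baseline testing, "their behavior on the selected behavioral metrics will be assayed and they will be randomized to an intervention group". There are four arms of 50 (SING, karaoke, curated playlists, pop music), run as "10 groups of 5 participants per intervention".

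The protocol states no expected Activity effect, Ownership effect or interaction, and no expected change in the three arms other than SING.

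**The concern.** The number and the analysis belong to different designs. The 0.01 is SING's own change from before to after. The R33 ANOVA asks whether change differs between active and passive arms, and between ownership and no-ownership arms. Every arm is measured before and after, so using change scores removes stable differences between people. Each person still receives only one intervention, so both factors and their interaction are compared between participants.

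This matters because R33 exists to separate the two factors, and item 3 (Background) names both as the active ingredients. A reader would take the 80% to cover the 2x2 analysis. If one factor's true effect is modest, a non-significant result for it would be likely, and could be misread as evidence that the factor does nothing.

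**Working it through.** **Inputs (item 13).** SING change 0.01; SD 0.02; two-sided 0.05; 80% power; four arms of 50. I take 0.02 as the SD of the change. The protocol's term (within-patient SD of the parameter estimates) is ambiguous, but this is the reading that reproduces 31. Changes are signed so that benefit is positive.

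**1. Reproducing 31.** One-group paired formula: n = (1.960 + 0.842)² × (0.02/0.01)² = 7.85 × 4 = 31.4. Other readings do not give 31: one-sided testing gives 25; 0.02 as the SD per occasion, with independent occasions, gives 63; a two-sample comparison of changes gives 63 per arm. By the exact paired t-test, 31 gives 76.8% power, 34 gives 80.8% and 50 gives 93.4%.

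**2. What the 2x2 tests.** Let S, K, C and P be the mean changes with SING, karaoke, curated playlists and pop music.

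- Activity = [(S+K) − (C+P)]/2
- Ownership = [(S+C) − (K+P)]/2
- Activity + Ownership = S − P, whatever K and C are
- Interaction = (S − K) − (C − P)

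If S = 0.01 and P ≥ 0, the two main effects sum to at most 0.01, so the smaller is at most 0.005.

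**3. Standard errors with n = 50 per arm.**

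- Main effect: 0.02/√50 = 0.00283
- SING versus one arm: 0.02 × √(2/50) = 0.0040
- Interaction: 0.02 × √(4/50) = 0.00566

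**4. Power (noncentral t, 196 df).** A main effect of 0.005 has noncentrality 0.005/0.00283 = 1.77 and power 42.1% (42.0% counting only the benefit direction). Other main effects: 0.0025, 14.2%; 0.0075, 75.1%; 0.0080, 80.4%; 0.01, 94.0%. The effects detectable with 80% power are 0.00796 (main), 0.01126 (SING versus one arm) and 0.01593 (interaction).

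The last column below follows closely from treating the two contrasts as independent. For the equal split, 1 − (1 − 0.421)² = 66%, and both are detected with probability 0.421² = 18%.

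| SING = 0.01, pop music unchanged | Larger factor | Smaller factor | At least one |
|---|---|---|---|
| Equal split, or SING alone changes | 42% | 42% | 66% |
| 0.0075 / 0.0025 | 75% | 14% | 79% |
| One factor carries all | 94% | 5% (no effect) | 94% |

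One factor must carry about 0.0080 of the 0.01 to reach 80%; the other is then 0.0020, with about 10% power. If pop music itself improves by 0.005 (assumed) and neither effect is negative, the larger factor has 14–42% and at least one is detected with 26–45%.

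**5. Reading 31 as per arm.** For a main effect of 0.01, 31 per arm gives 78.9% and 32 gives 80.1%. For 0.005, 31 per arm gives 28.2%.

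**6. Sensitivity of the 42% (each input assumed).**

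| Change | Power at 0.005 |
|---|---|
| 40 completers per arm | 35% |
| ICC 0.05 in groups of 5 (design effect 1 + 4 × 0.05 = 1.2) | 36% |
| Covariates explain 20% of the variance of change | 50% |
| SD of change 0.0283 | 24% |
| SD of change 0.0141 | 70% |

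Covariates would have to explain about 61% of the variance of change to reach 80%.

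**The case against.** The strongest reply is that 31 is not far wrong if read per arm. It gives 79% for a main effect of 0.01, the plan has 50 per arm, and the text speaks of a treatment difference without promising 80% for each factor. This is fair as far as it goes. But a main effect of 0.01 means that one factor carries SING's whole change, which the protocol does not say. With the pop-music arm not worsening, the other factor would then be zero or negative.

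Second, the Go/No Go Decision may let only large effects through. If its two-SD rule means a mean change of 0.04 (2 × 0.02, an assumption), an equal split gives 0.02 per factor and over 99% power. An equal split reaches 80% once SING changes by about 0.0159. This limits the scenario but does not remove it: the rule does not say whether it concerns the mean or individuals, and the R33 power paragraph plans on 0.01.

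Third, the 42% is for an unadjusted analysis, while item 8 makes medication a covariate in all analyses and the R33 Phase text promises balance on baseline performance. Adjustment could raise the power; drop-out and clustering would lower it.

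Finally, R33 is a mechanistic study with a reasonable chance of detecting something: 66–94% for at least one factor, if pop music is unchanged and neither effect is negative. That is correct. The shortfall concerns showing that both factors contribute.

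**Conclusion.** The concern holds. The only sample-size justification for the randomized phase is a one-group pre/post calculation carried over from R61, and the power it states does not belong to the 2x2 analysis it accompanies. On the protocol's own 0.01 and 0.02, 80% cannot hold for both Activity and Ownership, and the smaller has at most 42%.

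That ceiling assumes a SING change of 0.01, no worsening with pop music, 0.02 as the SD of change, 50 independent completers per arm, two-sided 0.05 and no covariate adjustment. It does not apply to SING versus a single arm, which has 70% power at a difference of 0.01; that is still below 80%, and it is not the planned main-effect test. The statement needs correcting before R33 relies on it.

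**What to change.** Keep n=200, the randomization and the analysis. Change only the wording of R33 Power to Detect Effects:

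1. Label 31 as the approximate size for the pre/post change within SING (exact paired t: 77% at 31, 81% at 34, 93% at 50). Say that 31 per arm supports a between-arm claim only for a main effect of 0.01 (79%).
2. Remove 31 as the general justification for the 2x2 ANOVA. State that using pre/post change reduces variance in every arm, but that Activity and Ownership remain between-participant contrasts.
3. State that 50 completers per arm give 80% power for a main effect of about 0.0080, a SING-versus-arm difference of about 0.0113 or an interaction contrast of about 0.0159. Add that a main effect of 0.005 (SING's 0.01 split equally, or SING alone changing, with pop music unchanged) has 42%.
4. State the assumptions: 0.02 is the SD of change, 50 completers per arm, independent participants, no covariate adjustment. Note that drop-out or clustering in groups of 5 lowers these powers, that the medication covariate may raise them, and that a different SD of change requires the figures to be restated.

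The cost is protocol text only, with no extra participants. The downside is that the stated R33 power becomes less favourable.
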